9.3 Clinical Laboratory Data

During the 6 weeks treatment period, clinical laboratory assessments in the fields of hematology, serum chemistry (including prolactin), and urinalysis will be conducted at the following scheduled visits: Day 1 (baseline), Week 4 and Week 6. HbA1c and TSH are only performed at baseline and Week 6.

Summary statistics for the routine clinical laboratory measurements, prolactin concentrations, HbA1c, and TSH at baseline, post-baseline visits, and changes from baseline will be provided. Incidence of potentially clinically significant abnormal lab results will also be summarized by treatment groups. Criteria of potentially clinically significant lab test abnormalities are provided in Appendix 1.

Shift tables will be produced assessing status (low-normal-high) changes from baseline.

Total bilirubin level should be checked for any subject with increased ALT or AST levels \geq 3 times the upper normal limits.

Liver injury related laboratory test results will be summarized for subjects who met following criteria, based on Hy's law lab criteria. The corresponding listing will be provided as well.

- AST or ALT \ge 3 × upper limit of normal (ULN) and
- $T_Bili \ge 2 \times ULN$

Prolactin data will be presented overall and by sex, and its change from baseline will be summarized.

9.4 Vital Signs Data

Descriptive statistics will be provided by treatment group, for both vital signs and change from baseline in vital signs. Vital signs include systolic blood pressure, diastolic blood pressure, heart rate in supine, sitting, and standing position. In addition, body weight, height, and waist circumference are measured. Body mass index (BMI) in kg /m² is calculated as weight in kilogram / (height in meter)².

Incidence of potentially clinically significant vital sign results will also be summarized by treatment groups. Criteria of potentially clinically significant vital sign abnormalities are provided in Appendix 2.

For a subject with several measures in either vital signs or Lab tests at a visit, the last repeat will be used in the by visit summary. However, for outlier analysis (such as

clinically significant abnormalities), data from all visits, no matter they are from the original visits, repeats, or unscheduled visits, will be included.

9.5 Body Weight, Waist Circumference and Body Mass Index

Analyses of body weight, waist circumference and BMI will be performed for the Safety Sample. Descriptive statistics based on observed cases data will be provided by trial weeks for change from baseline in body weight, as well as incidence of clinically significant changes in body weight, by baseline BMI status. Incidence of potentially clinically relevant weight gain will also be presented by region. Clinically significant changes are described in Appendix 1, Appendix 2 and Appendix 3 respectively. Descriptive statistics will also be summarized by visit for change from baseline in waist circumference and BMI.

9.5.1 Calculations of Z-scores for Body Weight, Height, and BMI

Age and sex adjusted z-scores for body weight and BMI will be calculated using the approach of the Center for Disease Control and Prevention (CDC), USA. The CDC provides a reference dataset (CDCref_d.sas7bdat in sas data format or CDCref_d.csv in csv data format) and a sas program (cdc-source-code.sas) along with detailed instructions for the calculations at

https://www.cdc.gov/nccdphp/dnpao/growthcharts/resources/sas.htm

Z-scores are calculated as Z = [((value / M)**L) - 1] / (S * L), in which "value" is the child's BMI, weight, height, etc. The L, M, and S values are in the reference dataset and vary according to the child's sex and age. The following rules will be observed:

- Age (in months) at the day of assessment, which is an input for the calculations, will be calculated as: (assessment date - birth date + 1)/(365.25/12).
- (2) In principle, BMI and its z-score will be calculated only if weight and height are both taken on the same day.

It is not anticipated that CDC's information (including the reference dataset or the SAS program or the instructions for the calculations) will be updated in the short run. Nevertheless, the information at the CDC website will be re-checked for any updates within a month prior to the interim database lock, and updated information will be used if any.

Mean changes in z-scores for body weight from baseline will be summarized by visit, and by sex, age category (< 15, ≥ 15 years) and region. Mean changes from baseline in z-scores for BMI will be summarized by visit. Furthermore, the number and percentage

of subjects with the change of body weight and BMI z-score (relative to baseline) ≥ 0.5 or ≤ -0.5 through Week 6 will be tabulated by treatment group.

9.6 Physical Examination Data

Physical examination findings will be listed by subject.

9.7 Electrocardiogram Data

ECG data will be summarized by mean change from baseline by treatment group by visit. For the analysis of QT and QTc, data from 3 consecutive complexes (representing 3 consecutive heart beats) will be measured to determine average values. The following QT corrections will be used:

- QTcF is the length of the QT interval corrected for heart rate by the Fridericia formula: QTcF=QT/(RR)^{0.33}
- 2) QTcN is the length of the QT interval corrected for heart rate by the FDA Neuropharm Division formula: QTcN=QT/(RR)^{0.37}

Incidence of potentially clinically significant treatment emergent ECG abnormalities will also be summarized by treatment groups. Criteria of potentially clinically significant ECG abnormalities are provided in Appendix 3.

9.8 Extrapyramidal Symptoms Scales

Change from baseline in each of the 3 EPS variables (SAS total score, AIMS total score, and BARS global clinical assessment score) will be summarized on the OC data by visit and on the LOCF data for the last assessment visit using descriptive statistics and ANCOVA model. In addition, BARS global clinical assessment will be treated as categorical variable taking values (categories) of "Absent", "Questionable", "Mild Akathisia", "Marked Akathisia" and "Severe Akathisia", and thus will be summarized on OC data by visit for each severity category, by using count and frequency.

Incidence of Treatment Emergent EPS-related AEs by EPS Category and MedDRA Preferred Term. The most up to date Otsuka list of EPR-related AEs at the time of the lock will be used.

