#### 3.7.3.5.3 Barnes Akathisia Rating Scale

The BARS (Appendix 12) consists of 4 items related to akathisia: objective observation of akathisia by the investigator, subjective feelings of restlessness by the subject, subjective distress due to akathisia, and global clinical assessment of akathisia. The first 3 items will be rated on a 4-point scale, with a score of zero representing absence of symptoms and a score of 3 representing a severe condition. The global clinical evaluation will be made on a 6-point scale, with zero representing absence of symptoms and a score of 5 representing severe akathisia. To complete this scale, subjects will be observed while they are seated and then standing for a minimum of 2 minutes in each position. Symptoms observed in other situations (eg, while engaged in neutral conversation or engaged in activity on the ward) may also be rated. Subjective phenomena are to be elicited by direct questioning. Anticholinergics, propranolol, benzodiazepines, and non-benzodiazepine sleep aids are not permitted within 12 hours of scale administration (see Section 4). Investigators are encouraged to delay scale administration until 12 hours have elapsed, if at all possible. However, if delaying administration of the scale is not feasible, the BARS should still be administered and the use of the medication documented, including a notation of the drug name, dose, and time of administration in eSource.

The BARS Global Score is defined as the global clinical assessment of akathisia.

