#### 7.6.5 Other Safety Data

Change from baseline in scores for the SAS, AIMS, and BARS scales will be evaluated using Analysis of covariance (ANCOVA) with baseline value as covariate and treatment as factor. The OC datasets of the Safety Sample will be used in the analyses of these EPS scales.

Suicidality monitored during the trial using the C-SSRS will be summarized as the number and percentage of subjects reporting any suicidal behavior, ideation, behavior by type (4 types), ideation by type (5 types), and treatment-emergent suicidal behavior and ideation, based on the Safety Sample.

Additional details about other safety data will be provided in the SAP.

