### Global clinical assessment of akathisia

- 0 *Absent*. No evidence of awareness of restlessness. Observation of characteristic movements of akathisia in the absence of a subjective report of inner restlessness or compulsive desire to move the legs should be classified as pseudoakathisia
- 1 *Questionable*. Non-specific inner tension and fidgety movements
- 2 Mild akathisia. Awareness of restlessness in the legs or inner restlessness worse when required to stand still. Fidgety movements present, but characteristic restless movements of akathisia not necessarily observed. Condition causes little or no distress
- 3 *Moderate akathisia*. Awareness of restlessness as described for mild akathisia above, combined with characteristic restless movements such as rocking from foot to foot when standing. Patient finds the condition distressing
- 4 *Marked akathisia*. Subjective experience of restlessness includes a compulsive desire to walk or pace. However, the patient is able to remain seated for at least five minutes. The condition is obviously distressing
- 5 *Severe akathisia*. The patient reports a strong compulsion to pace up and down most of the time. Unable to sit or lie down for more than a few minutes. Constant restlessness which is associated with intense distress and insomnia

Reproduced from: Barnes TR. A rating scale for drug-induced akathisia. Br J Psychiatry. 1989;154:672-6.

© 1989 The Royal College of Psychiatrists.

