9.10 Other Safety Data

Incidence of Onset of Akathisia Adverse Event by Week will be presented.

Incidence of sign/symptom items as recorded in the NY-AACENT scale will be summarized. Specifically, incidence (and severity) of the sign/symptom items will be tabulated by study visit, based on the OC data. The summarization will be repeated for the subset of drug-related signs or symptoms and for the subset of function impaired signs or symptoms, respectively. Additionally, change from baseline in the NYAACENT total score will be summarized on the OC data by study visit and on the LOCF data for the last assessment visit.

The UKU, NY-AACENT scale will also be summarized by week using the OC datasets of the Safety Sample.

The summary of Tanner Scale for OC datasets of the Safety Sample will be provided for week 6 and shift from baseline. The collection of Tanner Staging data is required for this trial, and every attempt will be made to collect this information. Tanner Staging will be completed together with the physical examination. When Tanner Staging is not completed at a required visit, it will be collected at the next trial visit. A subject who reaches Stage 5 (both in pubic hair and genitalia) does not need to continue with Tanner Staging.

The incidence of the individual side effects and categories of side effects recorded in the UKU will be summarized by treatment group for the Safety Sample by severity and causal relationship. In addition, the global assessment of side effects and the measures taken on the basis of the side effects will be summarized by incidence in a similar fashion to the above.

10 Scales: Rules for Scoring and Handling of Missing Data

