10.8 Barnes Akathisia Rating Scale (BARS)

The BARS⁸ consists of 4 items related to akathisia: objective observation of akathisia by the investigator, subjective feelings of restlessness by the subject, subjective distress due to akathisia, and global clinical assessment of akathisia. The first 3 items will be rated on a 4-point scale, with a score of zero representing absence of symptoms and a score of 3 representing a severe condition. The global clinical evaluation will be made on a 6-point scale, with zero representing absence of symptoms and a score of 5 representing severe akathisia.

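### The SAP's by-visit severity table for the BARS global assessment lists five of the scale's six levels and leaves out Moderate akathisia (score 3)

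*SAP*

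**What the plan says.** SAP 9.8 (Extrapyramidal Symptoms Scales) analyses the BARS global clinical assessment in two ways.

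- **As a number.** Change from baseline is analysed descriptively and by ANCOVA for the SAS total, the AIMS total and this item: "BARS global clinical assessment score) will be summarized on the OC data by visit and on the LOCF data for the last assessment visit". Protocol 7.6.5 plans the numeric analysis too: "Change from baseline in scores for the SAS, AIMS, and BARS scales will be evaluated using Analysis of covariance (ANCOVA").
- **As a category.** The same item is treated as categorical, "taking values (categories) of 'Absent', 'Questionable', 'Mild Akathisia', 'Marked Akathisia' and 'Severe Akathisia", and tabulated on observed-case data by visit, with a count and frequency for each severity category.

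The scale itself is described in three other places.

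- Protocol 3.7.3.5.3 describes the global item as a "6-point scale, with zero representing absence of symptoms and a score of 5 representing severe akathisia".
- SAP 10.8 agrees: "The global clinical evaluation will be made on a 6-point scale, with zero representing absence of symptoms".
- Protocol Appendix 12 names and defines every level from 0 to 5. Level 3, Moderate akathisia, reads: "Awareness of restlessness as described for mild akathisia above, combined with characteristic restless movements such as rocking from foot to foot when standing". It adds: "Patient finds the condition distressing".

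**The concern.** The category list in SAP 9.8 has five entries for an item with six possible values. A rating of 3 can be recorded at any visit but has no stated row, and no rule says how to handle it. A programmer following the text literally could leave it out of the rows, drop it from the table altogether, or place it in a neighbouring level. A programmer working from the collected 0 to 5 values could also simply restore the sixth row.

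The position of the gap matters. In Appendix 12, level 2 (Mild) is described as causing hardly any distress, and level 3 is the first at which the patient is distressed. Merging 3 into Mild would hide that boundary, and merging it into Marked would overstate severity. This table is the only by-visit distribution of BARS severity that the SAP plans, and change on the BARS is a named secondary safety endpoint (Protocol 3.5.2.2, SAP 6.2.2).

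**Working it through.** **Matching labels to levels**

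| Score | Protocol Appendix 12 | SAP 9.8 |
|---|---|---|
| 0 | Absent | Absent |
| 1 | Questionable | Questionable |
| 2 | Mild | Mild |
| 3 | Moderate | not listed |
| 4 | Marked | Marked |
| 5 | Severe | Severe |

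Scale levels: 6. Labels in SAP 9.8: 5. Unmatched: 6 − 5 = 1, namely score 3. Protocol 3.7.3.5.3 and SAP 10.8 anchor only scores 0 and 5 in words, but both give the number of points as six.

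**Is the omission deliberate?** Nothing suggests so. Neither SAP 9.8 nor SAP 10.8 pools levels. SAP 15 reports no changes to the planned analyses. The revision history in SAP 16 does not mention section 9.8. The August 2023 addendum adds analyses by race and ethnicity and leaves methods and conventions as they were. The sentence in SAP 9.8 is complete and shows no sign of redaction, so lost text is an unlikely explanation.

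**Ratings covered by the table.** BARS is scheduled at Weeks 1 to 6 (Protocol Table 3.7-1), with 105 subjects planned per arm (Protocol 7.1).

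- Per arm: 105 × 6 = 630 scheduled post-baseline ratings.
- Three arms: 630 × 3 = 1,890.

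These are upper limits on what the table covers, assuming every subject attends every visit. They do not count affected ratings.

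**Effect on one arm at one visit.** The documents give no rate for score 3. Assume k = 1, 3 or 5 subjects among 105, and for illustration 85 subjects rated Absent.

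| k | k/105 | Sum of listed rows if k stays in the denominator, (105 − k)/105 | Absent if k is dropped altogether, 85/(105 − k) |
|---|---|---|---|
| 1 | 0.95% | 99.05% | 85/104 = 81.7% |
| 3 | 2.86% | 97.14% | 85/102 = 83.3% |
| 5 | 4.76% | 95.24% | 85/100 = 85.0% |

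With all 105 subjects counted, Absent is 85/105 = 81.0%. If score 3 is instead folded into Mild or Marked, the rows sum to 100% and that row gains k subjects.

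**The case against.** The case for treating this as editorial is strong, and much of it stands. Read as a whole, the SAP points to six rows. SAP 10.8 gives a 6-point scale, SAP 9.8 asks for a summary of each severity category, and Appendix 12 supplies the missing name. No text supports pooling levels, so folding score 3 into Mild or Marked is only a possibility that the silence leaves open. A missing row with the denominator kept would show as soon as the counts failed to add up; only silent dropping or folding would pass that check. The illustrative counts are assumptions, and the 630 and 1,890 totals describe the table's coverage and say nothing about how many ratings are affected. The table shells are not in the documents, so they may already carry six rows.

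The consequence is also contained. The table is descriptive and has no test attached. Score 3 still enters the numeric summaries and the ANCOVA. Akathisia is reported elsewhere through EPS-related adverse events (SAP 9.8) and by timing of onset (SAP 9.10: "Incidence of Onset of Akathisia Adverse Event by Week will be presented"). It is also graded 0 to 3 on its own item in the UKU (Protocol Appendix 13), which SAP 9.10 summarises by week and by severity. The BARS table is therefore not the only graded view of akathisia over time.

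These points limit the weight of the matter but do not remove the discrepancy. The five-value list is the stated rule for the table, and it conflicts with the SAP's own description of the scale.

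**Conclusion.** The concern holds and is minor. As written, SAP 9.8 gives no category to score 3, Moderate akathisia, which contradicts Protocol Appendix 12, Protocol 3.7.3.5.3 and SAP 10.8. The size that can be taken from the documents is one of six levels unlisted in one descriptive safety table. The percentages shown above depend on the assumed 1 to 5 score-3 subjects per 105 and the assumed 85 rated Absent. They illustrate how the table could mislead and do not predict what it will show. The omission applies equally to brexpiprazole, aripiprazole and placebo, and no efficacy analysis is affected.

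**What to change.** In SAP 9.8, insert Moderate Akathisia between Mild Akathisia and Marked Akathisia, so that the list reads Absent (0), Questionable (1), Mild (2), Moderate (3), Marked (4), Severe (5). Check the table shell and add the row if it is not already there. The cost is two words in the SAP and at most one row in a table. No new data or analysis is needed.

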9.9 Columbia-Suicide Severity Rating Scale

Suicidality monitored during the trial using the C-SSRS will be summarized as the number and percentage of subjects reporting any suicidal behavior, ideation, behavior by type (4 types), ideation by type (5 types), and treatment-emergent suicidal behavior and ideation, based on the Safety Sample.

9.10 Other Safety Data

Incidence of Onset of Akathisia Adverse Event by Week will be presented.

Incidence of sign/symptom items as recorded in the NY-AACENT scale will be summarized. Specifically, incidence (and severity) of the sign/symptom items will be tabulated by study visit, based on the OC data. The summarization will be repeated for the subset of drug-related signs or symptoms and for the subset of function impaired signs or symptoms, respectively. Additionally, change from baseline in the NYAACENT total score will be summarized on the OC data by study visit and on the LOCF data for the last assessment visit.

The UKU, NY-AACENT scale will also be summarized by week using the OC datasets of the Safety Sample.

The summary of Tanner Scale for OC datasets of the Safety Sample will be provided for week 6 and shift from baseline. The collection of Tanner Staging data is required for this trial, and every attempt will be made to collect this information. Tanner Staging will be completed together with the physical examination. When Tanner Staging is not completed at a required visit, it will be collected at the next trial visit. A subject who reaches Stage 5 (both in pubic hair and genitalia) does not need to continue with Tanner Staging.

The incidence of the individual side effects and categories of side effects recorded in the UKU will be summarized by treatment group for the Safety Sample by severity and causal relationship. In addition, the global assessment of side effects and the measures taken on the basis of the side effects will be summarized by incidence in a similar fashion to the above.

10 Scales: Rules for Scoring and Handling of Missing Data

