The onset of schizophrenia symptoms typically peaks in late adolescence and early adulthood; however, prodromal symptoms may be present for several years before the initial psychotic episode. In a minority of cases, the initial episode may occur during childhood or early adolescence. Patients who experience this "early-onset schizophrenia" tend to exhibit symptoms that are more severe and follow a more chronic course. Whereas adults with schizophrenia typically experience exacerbations of psychotic symptoms between periods of relative normalcy, adolescents with schizophrenia may never achieve full remission of the initial episode. The prognosis for early-onset schizophrenia tends to be poor; cognitive impairment is greater compared with individuals whose onset of schizophrenia occurs later in life. In addition, refinement of social interaction skills that takes place during the teen years is interrupted, leading to a reduced ability for successful function in adulthood. Several antipsychotics have been investigated for the treatment of adolescent schizophrenia. Management of these subjects presents a particular challenge because developing bodies are more sensitive to side effects of antipsychotics, particularly with respect to weight gain.

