# 3.7.1.2 Baseline/Day 1 (Randomization)

If the subject is found to be eligible for the trial during the screening period, the subject will attend a baseline visit during which the following procedures will be completed prior to randomization:

- Inclusion/exclusion criteria will be verified. Review of inclusion/exclusion criteria at the baseline visit will be based on assessments performed during screening.
- Prior medications will be reviewed.
- A qualified and certified rater will administer the PANSS.
- A qualified rater will administer the CGAS.
- A qualified and certified rater will administer the CGI-S.
- The P-Q-LES-Q assessment will be completed by the subject.
- The investigator (or qualified designee) will complete the "Baseline/Screening" C-SSRS form.
- The investigator (or qualified designee) will administer the SAS, AIMS, and BARS.
- The investigator (or qualified designee) will administer the UKU and NY-AACENT.
- Body weight and waist circumference will be recorded.
  - Vital sign measurements (including blood pressure, body temperature, and pulse) will be recorded. Blood pressure and pulse are to be measured in the following order: supine, sitting, and standing after the subject has been in each position at least 3 minutes. Vital signs are to be completed before any blood is drawn.
- A standard 12-lead ECG will be performed predose after the subject has been supine and at rest for at least 5 minutes. The ECG is to be completed before any blood is drawn.
- Blood samples will be collected for clinical laboratory tests (hematology and serum chemistry [including blinded prolactin, HbA1c, and TSH]) after a minimum 8-hour fast, if fasting is possible. Vital sign and ECG assessments should be completed before any blood samples are collected.
- A urine pregnancy test will be performed predose for all females. The result must be negative prior to dosing.
- A serum pregnancy test will be collected for all females.
- Blood will be drawn for a plasma PK sample, which will be obtained 1–6 hours postdose, and the sampling time will be recorded.
- A pharmacogenomics (PGx) sample will be collected to determine the CYP2D6 metabolizer status.
- AEs and concomitant medications will be recorded.
- If the subject remains eligible for the trial after completion of the baseline evaluations, trial personnel will capture trial data within the eSource and randomize the subject to obtain an IMP assignment. The subject will receive the first dose of

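### SAP 9.10 does not limit UKU and NY-AACENT item incidence to symptoms new or worse than the pre-dose rating, so persisting baseline symptoms dilute the between-arm contrast

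*SAP*

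**What the plan says.** Both scales are listed as secondary safety endpoints (SAP 6.2.2). Protocol Table 3.7-1 schedules them at Screening, Day 1 and Weeks 1 to 6. On Day 1, among the procedures before randomization: "The investigator (or qualified designee) will administer the UKU and NY-AACENT".

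SAP 9.10 then plans the following.

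- **UKU.** "The incidence of the individual side effects and categories of side effects recorded in the UKU will be summarized by treatment group". The same sentence says that these "will be summarized by treatment group for the Safety Sample by severity and causal relationship". A separate sentence adds: "The UKU, NY-AACENT scale will also be summarized by week using the OC datasets of the Safety Sample".
- **NY-AACENT items.** "incidence (and severity) of the sign/symptom items will be tabulated by study visit, based on the OC data". Also: "The summarization will be repeated for the subset of drug-related signs or symptoms", with a further repeat for items that impair function.
- **NY-AACENT total.** "change from baseline in the NYAACENT total score will be summarized on the OC data by study visit", and also on LOCF data for the last assessment.

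SAP 10.10 scores a NY-AACENT item on whether it was present in the past week and how severe it was. Baseline status plays no part in the item score.

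**The concern.** The two scales are meant to describe side effects and cognitive adverse effects of treatment. Some of their items are also features of schizophrenia. NY-AACENT asks about attention and social cognition, and UKU includes emotional indifference and sleep duration. PANSS itself rates poor attention, blunted affect and social withdrawal. Subjects enter with a PANSS Total Score of at least 80, and the protocol's introduction says of early-onset illness that "cognitive impairment is greater compared with individuals whose onset of schizophrenia occurs later in life".

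A symptom recorded on Day 1 and unchanged at Week 6 therefore enters the item counts for the assigned arm exactly as a symptom that began on treatment does. A genuine increase in a side effect can then look like a small relative difference on top of a large shared background. For UKU the SAP also leaves open whether pre-dose records enter the incidence at all, so two programmers could produce different tables from the same data.

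**Working it through.** **Step 1. Compare with the SAP's other safety outcomes.**

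| Outcome | Treatment-emergent or baseline-referenced summary |
|---|---|
| Adverse events (SAP 9.2) | Yes: onset after trial drug, or a qualifying continuing event |
| SAS, AIMS, BARS (9.8) | Yes: change from baseline |
| C-SSRS (9.9) | Yes: a treatment-emergent category |
| Tanner (9.10) | Yes: shift from baseline |
| NY-AACENT total (9.10) | Yes: change from baseline |
| NY-AACENT items (9.10) | No |
| UKU (9.10) | No, and no incidence window stated |

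SAP 7.2 already defines baseline as the last measurement before the first dose. The rule needed exists but is not applied to these items.

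**Step 2. Size of the dilution.** The plan gives no figure for either scale, so there is nothing to reproduce. The rates below are assumptions; only n = 105 per arm comes from the documents.

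Let b be the share with the item at baseline (equal in the arms by randomization), s the share of those in whom it persists, and e the onset rate among those without it.

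- Any recorded = b·s + (1 − b)·e
- New onset, all subjects as denominator = (1 − b)·e
- 95% half-width of the difference = 1.96·√[(p₀(1 − p₀) + p₁(1 − p₁))/105]

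Take e = 10% on placebo and 25% on drug, with s = 1. Worked for b = 40%:

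- Any recorded: placebo 0.40 + 0.60 × 0.10 = 46%; drug 0.40 + 0.60 × 0.25 = 55%. Ratio 1.20, difference 9 points. Half-width 1.96·√[(0.2484 + 0.2475)/105] = 13.5 points.
- New onset: 6% and 15%. Ratio 2.50, difference 9 points. Half-width 1.96·√[(0.0564 + 0.1275)/105] = 8.2 points.

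| b | Any recorded, placebo vs drug | Ratio | New onset, placebo vs drug | Ratio | Difference, both | Half-width, any / new |
|---|---|---|---|---|---|---|
| 0% | 10% vs 25% | 2.50 | 10% vs 25% | 2.50 | 15 | 10.1 / 10.1 |
| 20% | 28% vs 40% | 1.43 | 8% vs 20% | 2.50 | 12 | 12.7 / 9.2 |
| 40% | 46% vs 55% | 1.20 | 6% vs 15% | 2.50 | 9 | 13.5 / 8.2 |
| 60% | 64% vs 70% | 1.09 | 4% vs 10% | 2.50 | 6 | 12.7 / 6.9 |
| 80% | 82% vs 85% | 1.04 | 2% vs 5% | 2.50 | 3 | 10.0 / 5.0 |

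A second set of assumptions gives the same picture. With b = 40%, s = 80% and onset 15% versus 5%, any recorded is 0.32 + 0.09 = 41% against 0.32 + 0.03 = 35%, a ratio of 1.17. New onset is 9% against 3%, a ratio of 3. The difference is 6 points both ways.

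**Step 3. Share of recorded drug-arm cases that are pre-existing**, b·s divided by any recorded, first set of onset rates: 50%, 73%, 86% and 94% for b = 20%, 40%, 60% and 80% with s = 1; 41%, 65%, 81% and 92% with s = 0.7.

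**Step 4. The equal-persistence assumption.** The two differences agree only if s is the same in both arms. With b = 40%, s = 1 on placebo (46%) and s = 0.7 on drug (0.28 + 0.15 = 43%), the any-recorded difference is −3 points while new onset is +9. That is still a valid randomized contrast, but it nets relief of illness symptoms against new symptoms.

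**The case against.** A reader might infer that these tables mostly report pre-existing illness and cannot show drug effects. The documents do not support either statement. The arms are randomized and blinded with a concurrent placebo, so a drug effect still appears, diluted. Whether most recorded items are pre-existing depends on a prevalence that is nowhere given: Step 3 runs from 41% to 94% on assumed inputs. Several UKU items, such as dystonia, tremor, akathisia and paraesthesias, are not shown to be illness symptoms.

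The other side has further fair points.

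- **NY-AACENT is partly covered** by the total-score change, the severity display and the drug-related and function-impaired repeats. SAP 3.4 counts Day 1 as a scheduled scale visit, so the by-visit table may already show Day 1 prevalence. This stands, but marginal prevalences do not show which subjects are new cases, and a total can hide a new problem in one item behind improvement in others.
- **UKU is split by causal relationship.** This helps, but it rests on the rater's attribution, which is hardest to make for items that resemble the illness.
- **Treatment-emergent adverse events are analysed in SAP 9.2.** True, but those come from a non-leading question (Protocol 5.2), whereas UKU is gone through item by item.
- **No test is planned for either scale**, so power figures would describe nothing in the SAP. I accept this and use interval widths.
- **Both scales were added to meet regulatory requirements, and NY-AACENT is not validated** (Protocol 3.7.3.5.4 and 3.7.3.5.5). This limits the weight of the point; it does not justify an ambiguous table.

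**Conclusion.** The concern holds as a dilution and a definition gap. Item-level incidence for UKU and NY-AACENT has no new-or-worse rule, unlike the SAP's other safety outcomes in Step 1. In the illustration, baseline prevalence of 20% to 80% pulls a ratio of 2.50 down to between 1.43 and 1.04. The confidence half-width is roughly 1.4 to 2 times as wide as for new onset (12.7/9.2 to 10.0/5.0). The risk difference is unchanged if persistence is equal in the arms.

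These sizes rest on assumed onset, prevalence and persistence, and on 105 analysed subjects per arm; the direction of the dilution does not depend on the particular values. UKU is the weaker of the two, with no baseline-referenced summary and no stated window. No efficacy conclusion is affected.

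**What to change.** In SAP 9.10:

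1. For both scales, tabulate by treatment group the items newly present, or worse in severity, than the last pre-dose rating. Use as denominator all Safety Sample subjects with a baseline and at least one post-baseline rating.
2. Show the baseline prevalence of each item alongside.
3. State that UKU incidence counts post-dose ratings only.
4. Keep the planned by-visit and causality tables as supportive.

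The baseline ratings are already collected. The cost is SAP wording, programming and one additional descriptive table per scale.
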